4.2.12 Exploratory Objective 7, Exploratory research

This will not be reported in the CSR.

4.3 Pharmacodynamic Endpoints

Details for these endpoints are described in Section [4.2](#).

4.4 Pharmacokinetics

Details are provided in Section [4.2.6](#).

4.5 Immunogenicity

Not applicable.

4.6 Safety Analyses

The domain safety covers exposure, adverse events, clinical laboratory, vital signs, and ECG.

The estimand attributes Population and Treatment are the same as for key and exploratory objectives, see definition in section [4.2](#). The main Intercurrent event strategy is Treatment policy. Attributes Endpoint is defined in [Table 8](#)

Intercurrent event strategies:

Treatment policy strategy

In general the treatment policy strategy will be used e.g. for premature treatment discontinuation due to any reason or prohibited medication. Then measurements for the variables of interest will be collected and analysed regardless of intercurrent events. For terminal events (i.e. death) a while-alive strategy will be applied unless death is one of the events being analysed e.g. for AEs then it will be included.

Population summary:

Descriptive statistics presenting distribution of endpoints by treatment group. For continuous variables the mean will be used and for categorical n and % will be used.

Table 8 Safety objectives

Statistical / Estimand category	Endpoint	Population/Analysis set	Intercurrent event strategy	Population level summary (analysis)	Details in section
Safety objective: To assess the safety and tolerability of zibotentan/dapagliflozin and zibotentan versus placebo.					
Primary analysis	
 • AEs, SAEs, and DAEs • AESIs CCI • Vital signs • Safety laboratory tests • ECG assessments 	
Estimand population: See above for respective arms.
 
Analysis set: FAS
	Treatment policy strategy	See above.	4.6

4.6.1 Exposure

4.6.1.1 Definitions and Derivations

The duration of exposure (days) will be calculated as: date of last dose – date of first dose +1.

4.6.1.2 Presentation

Duration of exposure will be summarised by treatment group and total number of subjects and will be presented as a continuous variable with descriptive statistics.

Listing presenting individual exposure will be provided.

4.6.2 Adverse Events

4.6.2.1 Definitions and Derivations

For Adverse events of special interest see section [4.6.8](#).

The definitions and information on collection of AEs and SAEs can be found in CSP. All AEs will be classified by SOC and PT according to a MedDRA. Only AEs occurring with an onset date, or worsening, on or after first dose of study intervention, throughout the treatment period and including the follow-up period will be presented in summary tables

The following definitions and principles are to be followed:

AE

AE reported with an onset date within the defined analysis period.

SAE

SAE where the onset date of the premediating AE belongs to the analysis period, irrespectively of the date the AE becomes serious.

SAEs with outcome of death

Defined as SAE with reported outcome as “fatal”, there may be more than one AE with outcome death for a subject. The onset date of the AE determines the analysis period, irrespective of date of death.

AEs leading to discontinuation of IP

Defined as an AE with action taken study intervention reported as drug permanently discontinued. The onset date of the AE determines the analysis period, irrespectively of date of discontinuation of study intervention.

AEs leading to interruption of IP

Defined as an AE with action taken study intervention reported as drug interrupted, permanent discontinuations is not included.

AEs possibly related to IP

Defined as an AE that is reported by the investigator as “reasonable possibility AE caused by IP”. If this causality evaluation is missing, it will be counted as an AE possible related to study intervention.

AEs by maximum intensity

AEs will be classified by the reported maximum intensity (mild, moderate, and severe). If the maximum intensity evaluation is missing, it will be counted as “Severe”. If a subject has multiple AEs within the same category of different intensities, the more severe intensity will be considered in the presentations.

4.6.2.2 Presentation

The number and percentage of subjects with AEs will be tabulated by treatment group. For subject count presentations, subjects will only be counted once per category, regardless of the number of AEs satisfying the condition.

The following summaries will be presented:

Overall summary of AEs

Number of subjects with any AE, any SAE, any AE with outcome of death, any AE leading to discontinuation of IP, any AE leading to interruption of IP, any AE possible related to IP and any AESIs (see section 4.6.8) will be presented. This will also be presented for Japanese sub-population.

By SOC and PT

Separate AE tables by SOC and PT will be provided for: Any AE, any SAE, any AE with outcome of death, any AE leading to discontinuation of IP, any AE leading to interruption of IP and any AE possible related to IP. AE table by SOC and PT for any AE will also be presented for Japanese sub-population. Event count table will be presented for AEs and SAEs by SOC and PT.

By PT

Separate AE table sorted by decreasing frequency on PT level will be presented.

Maximum intensity

AEs will be presented by their maximum intensity for all AE and by PT.

Most common non-serious AEs

A table of non-serious AEs occurring in more than 5% of subjects in any treatment group will be presented by SOC and PT.

Assessment of potential proarrhythmic effect

A table with number and percentage of subjects with PTs relevant for assessment of potential proarrhythmic effect will be presented. PTs are based on the SMQ Torsade de pointes/QT prolongation (narrow and broad scope).

Key subject information

Key subject information for subjects with SAEs, AEs with outcome death and AEs leading to discontinuation of IP will be provided.

Key subject information will also be presented for subjects with modified Hy's law during the study, if appropriate a summary table will be produced.

Listings and narratives

An AE listing including individuals in FAS covering details for each individual AE will be produced. An AE listing for participants who were randomized but not exposed to study intervention is presented separately. SAEs occurring prior to start of study intervention will be included in data listings. Narratives may also be produced.

4.6.3 Clinical Laboratory, Blood Sample

4.6.3.1 Definitions and Derivations

Blood samples for determination of clinical laboratory assessments are collected according to the CSP. Clinical laboratory assessments of blood samples, including electrolytes, will be categorised into haematology, chemistry and coagulation parameters as defined below in [Table 9](#).

Table 9 Clinical blood laboratory parameters

Haematology	
White blood cell count	Lymphocytes absolute count
Red blood cell count	Monocytes absolute count
Haemoglobin	Eosinophils absolute count
Haematocrit	Basophils absolute count
Neutrophils absolute count	Platelet absolute count
Chemistry	
BUN	Alanine aminotransferase
Creatinine and calculated eGFR (CKD-EPI) and eGFR2	Aspartate aminotransferase
Total bilirubin and direct bilirubin	Alkaline phosphatase
Albumin	Creatine kinase
Calcium	Serum glucose
Phosphate	Gamma-glutamyl transferase
Serum Osmolality	NT-pro BNP
Bicarbonate (HCO ₃ ⁻)	Sodium
Chloride (Cl ⁻)	Potassium
Magnesium (Mg ⁺)	
Coagulation	
International normalised ratio	Prothrombin time
Partial thromboplastin time	

Assessed values of the form ‘<x’ (below the lower limit of quantification) or ‘>x’ (above the upper limit of quantification) will be imputed as ‘x’ in calculation of summary statistics but displayed as ‘<x’ or ‘>x’ in listings.

Treatment emergent

A treatment emergent abnormality is defined as either of below:

- A switch in parameter from normal at baseline to abnormal at post-baseline accordingly to predefined criteria, see below for predefined criteria.
- A baseline value that met the criteria for abnormality and the post-baseline value is more extreme (further from the limit), see below for predefined criteria.

When the predefined criteria for a parameter abnormality is referring to ULN then this is based on reference ranges from the central laboratory. For some parameters there are different criteria for the same parameter that can be separately fulfilled and will be presented separately.

Predefined criteria for Haematology

Platelet absolute count ($10^9/L$): <50, <75

Predefined criteria for Chemistry

NT-pro BNP (pg/mL): >1 x 125, >2 x 125, >5 x 125

Alanine aminotransferase (U/L), Alkaline phosphatase (U/L), Aspartate aminotransferase (U/L): >1 x ULN, >3x ULN, >5 x ULN

Direct bilirubin (mg/dL): >1 x ULN, >2x ULN, >3x ULN

Total bilirubin (mg/dL): >1 x ULN, >2x ULN, >5 x ULN

Alkaline phosphatase (U/L): ≥ 2 x baseline

Alanine aminotransferase (U/L), Aspartate aminotransferase (U/L): ≥ 2 x baseline and > 1 x ULN

Direct bilirubin (mg/dL): ≥ 1 mg/dL over baseline

Total bilirubin (mg/dL): ≥ 2 x baseline and > 2 x ULN

Combination criteria: Aspartate aminotransferase (U/L) or Alanine aminotransferase (U/L) ≥ 3 x ULN and Total bilirubin (mg/dL) > 2 x ULN

Predefined criteria for Coagulation

INR: $> 0.2 +$ Baseline, $> 0.4 +$ Baseline, $> 0.6 +$ Baseline

Shift table definitions

Below parameters will be categorised according to below categories for the shift tables.

Haematology, shift from baseline to minimum value

Platelets ($10^9/L$) with categories: <50, ≥ 50 - < 75 , ≥ 75 - < 150 , ≥ 150 - < 400 , ≥ 400

Chemistry, shift from baseline to maximum value

Alanine aminotransferase (U/L), Alkaline phosphatase (U/L), Aspartate aminotransferase (U/L), Direct bilirubin (mg/dL), Total bilirubin (mg/dL) with categories: Normal(\leq ULN), High ($> 1 \times$ ULN and $\leq 2 \times$ ULN), Higher ($> 2 \times$ ULN and $\leq 5 \times$ ULN), Highest ($> 5 \times$ ULN). N-Terminal proB-type natriuretic peptide (pg/mL) with categories: Normal($\leq 1 \times 125$), High ($> 1 \times 125$ and $\leq 2 \times 125$), Higher ($> 2 \times$ ULN and $\leq 5 \times 125$), Highest ($> 5 \times 125$).

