Vital signs (supine and standing blood pressure and pulse)	X	X (pre-dose) X (60, 120, 180 minutes)	X	X	X	X	X		Section 8.3.2
Body temperature	X	X	X	X	X	X	X		Section 8.3.2

Table 1 Schedule of Activities

	Screening period	Treatment period						Follow-up	Section in the CSP
		Randomisation	Visits						
Visit number	1	2	3	4	5	6 ^a	7		
Week	-3	0	1	2	3	6	8		
Study day	-21 to -7 ^a	1	8	15	22	43	57		
Visit window (days)			± 3	± 3	± 3	± 5	± 3		
Clinical safety laboratory tests (haematology, clinical chemistry, coagulation, electrolytes, serum osmolality, and NT-pro BNP)	X	X ⁱ	X ⁱ	X ⁱ	X ⁱ	X ⁱ	X	Section 8.3.5	
PK assessments									
Pre-dose PK plasma sample (all participants) ^j			X ⁱ	X ⁱ	X ⁱ			Section 8.5	
PK profile (Japanese)					X ^{k,1}			Section 8.5	
Post-dose sample (Non-Japanese)					X ^m			Section 8.5	

Table 1 Schedule of Activities

	Screening period	Treatment period						Follow-up	Section in the CSP
		Randomisation	Visits						
Visit number	1	2	3	4	5	6 ^a	7		
Week	-3	0	1	2	3	6	8		
Study day	-21 to -7 ^a	1	8	15	22	43	57		
Visit window (days)			± 3	± 3	± 3	± 5	± 3		
Exploratory assessments									
CCI	X ^g					X ^{fg}			Section 8.2.2.1
eGFR calculation ^a	X	X	X	X	X	X	X		Section 8.2.2.2
MELD score calculation	X	X	X	X	X	X	X		Section 8.2.2.3
Child-Pugh score	X	X	X	X	X	X	X		
Non-fasting plasma/serum biomarkers		X ⁱ			X ⁱ	X ⁱ			
HbA1c	X ⁱ	X ⁱ			X ⁱ	X ⁱ			
PROs: CLDQ, PGIS - Liver Disease, and SF-36v2 acute		X ^o				X			Section 8.2.2.4
Collect and store serum and plasma samples for exploratory assessment of biomarkers		X ⁱ				X ⁱ			Section 8.8.1

Table 1 Schedule of Activities

	Screening period	Treatment period						Follow-up	Section in the CSP
		Randomisation	Visits						
Visit number	1	2	3	4	5	6 ^a	7		
Week	-3	0	1	2	3	6	8		
Study day	-21 to -7 ^a	1	8	15	22	43	57		
Visit window (days)			± 3	± 3	± 3	± 5	± 3		
Collect and store urine samples for exploratory assessment of biomarkers		X ⁱ				X ⁱ			Section 8.8.1
Optional Genomics Initiative, exploratory genomics, and multi-omics samples		X							Section 8.7 and Appendix D

- Screening visit can take place from 21 days up to 7 days before randomisation visit (Visit 2). It must be at least 7 days between Visit 1 and Visit 2 to allow time for laboratory results to be examined.
- Brief physical examination.
- Only in those participants with history of Heart Failure and if historical data from ECHO or cardiac MRI in the prior 12 months is not available.

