3.3.1 General Study Level Definitions

3.3.1.1 Baseline

For alanine aminotransferase (ALT), aspartate aminotransferase (AST), total bilirubin, direct bilirubin, alkaline phosphatase (ALP) and international normalized ratio (INR) baseline is defined as the mean of the values obtained during the screening period including unscheduled visits and the day of first dose.

For ECG and vital signs, baseline is defined as the last non-missing value prior to first administration of dose i.e. post-dose assessment on the day of first administration is not to be used.

The baseline value will for all other data be defined as the last non-missing value prior to or on the same date as administration of the first dose, unless values on the same date are known to be both pre- and post-dose assessments in which case the pre-dose assessment will be used as baseline.

For Loop diuretic baseline definition see section [3.3.1.5](#).

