3.3.2 Visit Window

For the purpose of analysing visit based data, analysis visit windows will be used and are based on first dose date. All scheduled and unscheduled visits occurring the day after first dose or later (including Early Termination visit), will be mapped to an appropriate visit. Unless specified otherwise visit based analyses will follow as shown in [Table 4](#).

Table 4 General visit windowing

Analysis visit label	Analysis visit window start day (day included) ^a	Analysis visit window end day (day included) ^a	Target Day ^a
Week 1	Day 2	Day 11	Day 8
Week 2	Day 12	Day 18	Day 15
Week 3	Day 19	Day 31	Day 22
Week 6	Day 32	Day 50	Day 43
Week 8	Day 51	Day 78	Day 57

a Relative to the date of first dose of study treatment.

For general visit based-summaries, if there is more than one value per subject within a visit window, the closest assessment to the target date is assigned, or the earliest in the event the values are equidistant from the nominal visit date.

Composite endpoints (key objective 1,2,7 and 8) will follow [Table 5](#).

Table 5 Composite endpoints visit windowing

Analysis visit label	Analysis visit window start day (day included) ^a	Analysis visit window end day (day included) ^a
Week 1	Day 1 for component of fluid retention AEs Day 2 for other components	Day 11
Week 2	Day 12	Day 18
Week 3	Day 19	Day 25
Week 6	Day 26	Day 48
Week 8	Day 49	Each subjects EOS ^b

a Relative to the date of first dose of study treatment.

b Given that EOS occurs on or after study day 49.

Data that has been collected daily (loop-diuretic and home weight) will be summarized using visit windowing presented in [Table 6](#).

Table 6 Home weight and Loop-diuretic visit windowing

Analysis visit label	Analysis visit window start day (day included) ^a	Analysis visit window end day (day included) ^a
Week 1	Day 2	Day 8
Week 2	Day 9	Day 15

Analysis visit label	Analysis visit window start day (day included) ^a	Analysis visit window end day (day included) ^a
Week 3	Day 16	Day 22
Week 4	Day 23	Day 29
Week 5	Day 30	Day 36
Week 6	Day 37	Day 43
Week 8	Day 44	Each subjects EOS ^b

a Relative to the date of first dose of study treatment.

b Given that EOS occurs on or after study day 49.

In general, for summaries of extreme data at a subject level, all observations will be included regardless of whether it is included in the by-visit data presentation, e.g. when deriving a statistic such as the maximum.

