4.6.3.2 Presentations

All laboratory data will be presented in SI or conventional units.

The haematology, chemistry and coagulation parameters defined in [Table 9](#) will be presented as continuous variables using descriptive statistics as specified in section [3.3](#) and will be presented by treatment group and by scheduled post-baseline visits for observed values and change from baseline.

The number of subjects with treatment-emergent laboratory parameter abnormalities will be presented categorically by treatment group. Only the most extreme value per subject will be accounted for.

Shift tables from baseline to maximum or minimum value will also be presented by treatment group. For INR summary table for maximum on study value as compared to baseline will be presented.

Scatter plot of maximum ALT or AST versus maximum total bilirubin and corresponding tabulation will be presented as well.

Key subject information will be presented for subjects with treatment emergent abnormalities for haematology, chemistry or coagulation abnormalities.

Additional key subject information and graphs of individual data will be presented including laboratory parameters which are associated with liver safety. This will be done for e.g. subjects with investigational product interruptions and discontinuations, subjects with DILI/modified Hy's Law.

Supportive laboratory listings will cover observed values and changes from baseline for each individual participant as well as abnormalities as compared to laboratory reference ranges.

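### For participants already abnormal at baseline, any worsening counts as treatment-emergent, so noise alone flags most of them in the lowest-threshold laboratory and vital-sign rows

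*SAP*

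**What the plan says.** SAP 4.6.3.1 defines a treatment-emergent laboratory abnormality in two ways. The first is a move from normal at baseline to abnormal afterwards. The second is "A baseline value that met the criteria for abnormality and the post-baseline value is more extreme (further from the limit"). SAP 4.6.6.1 repeats both for vital signs.

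SAP 4.6.3.2 adds, for the laboratory table, "Only the most extreme value per subject will be accounted for". SAP 3.3.2 says that for participant-level extremes "all observations will be included regardless of whether it is included in the by-visit data presentation", so unscheduled values count too.

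The criteria touched by the second route are fixed limits, each with its own row. Examples are "Total bilirubin (mg/dL): >1 x ULN, >2x ULN, >5 x ULN" and "NT-pro BNP (pg/mL): >1 x 125, >2 x 125, >5 x 125". ALT, AST, ALP and direct and total bilirubin also have baseline-relative rows, such as at least 2 x baseline. INR has only baseline-relative rows. Platelets (<50, <75) and NT-proBNP have fixed limits only.

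SAP 3.3.1.1 sets the comparator. For ALT, AST, bilirubin, ALP and INR, "baseline is defined as the mean of the values obtained during the screening period including unscheduled visits and the day of first dose". For NT-proBNP and platelets it is "defined as the last non-missing value prior to or on the same date as administration of the first dose".

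The laboratory flags also decide who gets key subject information (SAP 4.6.3.2).

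**The concern.** The worst of several later values is compared with one baseline value or a short average, and a difference of any size counts. Ordinary fluctuation will usually produce a worse value somewhere among five visits. The count for baseline-abnormal participants therefore mostly measures noise and number of visits, in all three arms alike.

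Three things are at stake. First, the row total mixes participants who became abnormal with participants who were abnormal and fluctuated, and no denominator by baseline status is specified. Second, once most baseline-abnormal participants are flagged in every arm, a harm confined to a few has little room to show. Third, individual review through key subject information fills with trivial changes.

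The point matters most for NT-proBNP. Fluid retention and heart failure are named zibotentan risks (Protocol Table 2), and NT-proBNP has no baseline-relative row.

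**Working it through.** The plan gives no expected rate for this rule, so there is no figure to reproduce.

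**Inputs from the documents**
- Post-baseline draws, k = 5: Visits 3 to 7 (Weeks 1, 2, 3, 6, 8) on the Protocol 1.3 line "Clinical safety laboratory tests (haematology, clinical chemistry, coagulation, electrolytes, serum osmolality, and NT-pro BNP"). If Week 8 is left out, k = 4.
- Baseline values averaged: m = 2 for liver tests (Visits 1 and 2); m = 1 for NT-proBNP and platelets.
- Arm size: 22.

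**Assumptions (not in the documents)**
- Within-person fluctuations are independent, and there is no drug effect.
- Intraclass correlation (ICC, the share of total variance that lies between people): 0.5 to 0.95.
- Prevalence of an abnormal baseline: 10% to 70%.

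**Step 1, closed form.** With one baseline value and k exchangeable later values, P(worst later value is beyond baseline) = k/(k+1). This is 5/6 = 83.3% for k = 5 and 4/5 = 80.0% for k = 4.

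**Step 2, condition on an abnormal baseline.** The rule applies only to people selected for a high baseline, so regression to the mean pulls the rate down. Simulation with a normal random person effect, k = 5:

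| Baseline | Lowest cell (ICC 0.5, prevalence 10%) | ICC 0.8, prevalence 50% | Highest cell (ICC 0.95, prevalence 70%) |
|---|---|---|---|
| m = 2 (liver tests) | 68.5% | 85% | 88% |
| m = 1 (NT-proBNP, platelets) | 47% | 76% | 81% |

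With k = 4 the ranges are 63% to 84% (m = 2) and 42% to 78% (m = 1).

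**Step 3, in participants.** If 11 of 22 start abnormal (m = 2, ICC 0.8), noise flags 11 x 0.847 = 9.3 of them. The chance that more than half of the 11 are flagged is 99.7%.

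**Step 4, what the row can still show.** Log-normal values, within-person CV 20%, ICC 0.8, 50% abnormal at baseline, m = 2, k = 5. With no effect, 83.3% of baseline-abnormal and 42.4% of baseline-normal participants are flagged, so the row is 0.5 x 83.3 + 0.5 x 42.4 = 62.9%. The second route alone supplies 0.5 x 83.3 = 41.7 points.

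| Assumed drug effect | Row under the SAP rule | Row for at least 2 x baseline and beyond the limit |
|---|---|---|
| None | 63% | 1% |
| Value tripled in 20% of participants | 70% | 21% |
| 1.2-fold rise in all | 82% | 6% |
| 1.5-fold rise in all | 93% | about 35% |

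Under the minority effect, the baseline-abnormal flag rate moves only from 83% to 87%. As a yardstick only, since no test is planned, a one-sided 5% Fisher comparison of 22 v 22 would detect that effect with 7% power from the SAP row and 45% from the 2 x row.

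**Step 5, which rows are exposed.** The second route needs a baseline beyond the limit. Protocol 5.2 excludes ALT or AST of 150 U/L or more, total bilirubin of 3 x ULN or more, platelets below 50, systolic pressure below 95 and diastolic pressure below 60. Few or no participants should therefore start abnormal in the total bilirubin >5 x ULN, platelet <50, low supine pressure and higher ALT/AST rows (the last depends on the laboratory's ULN, which is not given). Still exposed are the >1 x ULN rows, total bilirubin >2 x ULN, all NT-proBNP rows (no entry limit is visible), platelets <75, high supine pressure and out-of-range weight. INR is untouched, because a baseline cannot meet a criterion defined relative to itself.

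**The case against.** The strongest reply is that these are descriptive tables in a study of 22 per arm with no formal tests, and that the SAP shows the same data in other ways. A participant who moves from >1 to >3 x ULN already counts in the >3 row. Liver tests have baseline-relative rows. Shift tables cross baseline category with the worst value for liver tests, platelets and NT-proBNP. By-visit change from baseline, an ALT/AST against bilirubin scatter plot, individual graphs and listings are planned, and supine blood pressure is a key endpoint analysed by MMRM.

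Most of this stands for liver tests. It stands less well for NT-proBNP and platelets. Their shift categories hide change within a category: a platelet fall from 74 to 51 stays in one cell, and the top NT-proBNP category is open-ended. By-visit means can hide an effect in a few participants.

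It is also fair that Protocol Appendix E 1 expects abnormal and fluctuating values for liver tests only. Nothing in the documents says how common abnormal NT-proBNP or platelet baselines will be.

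A reader might infer that the tables will look alike in all arms whatever the drug does. The documents do not support that: Step 4 shows a uniform 1.5-fold rise taking the row from 63% to 93%. A reader might also infer that every threshold and every vital sign is affected. The entry criteria rule that out (Step 5).

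**Conclusion.** The concern holds in a limited form. The second route has no minimum change and, for laboratory data, is explicitly judged on the most extreme value. SAP 4.6.6.2 does not say which value is used for vital signs, but a rule that any worse later value satisfies has the same effect. Noise alone flags about 68% to 88% of baseline-abnormal participants for liver tests and about 47% to 81% for single-baseline parameters. The rate falls below half only in the corner with low ICC and few abnormal baselines.

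The consequence is loss of contrast in the lowest-threshold rows and the NT-proBNP rows for an effect confined to a minority, plus clutter in key subject information. It is not a general masking of drug effects.

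The ranges rest on assumed ICC, CV and prevalence and on independent fluctuations. Positive correlation between neighbouring visits would lower the rates somewhat; unscheduled draws would raise them.

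**What to change.** 1. In the treatment-emergent tables of SAP 4.6.3 and 4.6.6, report new abnormality (normal at baseline) and worsening (abnormal at baseline) in separate rows. Give each a denominator of participants with that baseline status.
2. Add for NT-proBNP and platelets a prespecified baseline-relative row like those already used for liver tests. The sponsor should fix the multiple before unblinding, with assay and within-person variability in view. For illustration, with m = 2 and ICC 0.8, a 2 x baseline rule flags 0%, 0.5% and 7% of baseline-abnormal participants by noise at CV 10%, 20% and 30%. With a single baseline value at CV 20% it flags 1%.
3. For baseline-abnormal participants, trigger key subject information from the baseline-relative row or from first reaching a higher criterion, not from any worsening.
4. Keep the any-worsening count as its own row, so no information is lost.

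Reaching the next listed cut-off should not replace the worsening rule on its own. Vital signs have one limit on each side, and the top laboratory rows have no next step: NT-proBNP rising from 630 to 5000 pg/mL would never count.

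The cost is SAP wording, table programming and a few more rows. No data collection changes. Splitting the rows does not remove the noise that carries baseline-normal participants across a limit, but it shows that count against its own denominator.
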